Appendix III. Prohibited Drug List (Continued)

	Drug Category	Major Indications	Type of Impact	Description of Impact	Route	Brand Name	Generic Name	Washout Period*		
40	Monoamine Oxidase-A Inhibitor	Major depression	PK/ Safety	↑PK and cardiac side effects of Primatene and Albuterol	PO	Marplan Nardil Parnate Eldepryl Zelapar Xadago	Isocaarboxazid Phenelzine Tranylcypromine Selegiline Selegiline Safinamide	14 days		
41										
42										
43	Monoamine Oxidase-B Inhibitor	Parkinsonism								
44										
45										
46	Oral Decongestant /Oral or Parenteral Sympathomimetics	Attention Deficit Hyperactivity Disorder (ADHD)	PK/ Safety	↑PK level and ↑cardiac side effects of Primatene and Albuterol	PO	Adderall Adderall XR Dexedrine Ritalin Ritalin LA Vyvanse	Dextroamphetamine mixed salts Dextroamphetamine Methylphenidate Methylphenidate Lisdexamfetamine	2 days 5 days 4 days 2 days 5 days 1 day		
47						Adrenalin	Epinephrine	1 day		
48						Afrin Neo-synephrin	Oxymetazoline Phenylephrine	2 days 1 day		
49		Anaphylaxis			PO	Advil Cold & Sinus	Ibuprofen/ Pseudoephedrine	1 day		
50						Allegra D	Fexofenadine/ Pseudoephedrine			
51						Claritin D	Loratadine/ Pseudoephedrine			
52		Nasal Congestion			PO	Mucinex D	Guaifenesin/ Pseudoephedrine			
53						Sudafed/PE	Phenylephrine			
54						Sudafed/SA	Pseudoephedrine			
55		Allergy/nasal congestion			PO	Zyrtec D	Cetirizine/ Pseudoephedrine			
56										
57										
58		Allergy/Nasal & Chest Congestion			PO					
59										
60										
61										
62	Phenothiazines	Nausea & Vomiting	Safety	May potentiate side effect of Primatene and Albuterol	PO	Compazine	Prochlorperazine	7 days		
63						Etrafon*	Perphenazine/ amitriptyline			
64		Schizophrenia			PO	Mellaril*	Thioridazine			
65						Serentil*	Mesoridazine			
66						Stelazine*	Trifluoperazine			
67					PO/IV	Thorazine*	Chlorpromazine			
	Thyroid hormones	Hypothyroidism	Safety	↑ cardiac effects of Primatene and Albuterol	PO	Synthroid	Levothyroxine	6 weeks		

*This drug list is provided based on the drug interaction listed in package insert of Epi-Pen. Some drugs that have been discontinued per FDA website will not be listed here. Asthma medications are also not listed because this study is for healthy volunteers only.

Appendix IV. Blood Metabolic/CBC and Urinalysis Tests

Based on the ICH guidelines (i) Guideline for Good Clinical Practice E6 (R1), version 4, dated 10 June 1996; and (ii) Safety Pharmacology Studies for Human pharmaceuticals S7A, version 4, dated 8 November 2000. For safety assessment, the following items will be conducted at screening.

#	Test Categories	Description	#	Test Items	*Reference Normal Range	Footnote
1	Comprehensive Metabolic Panel	≥ 8 hr fasting	1	Total protein	6.2 to 8.3 g/dL	Albumin/globulin
			2	Sodium	133 to 145	
			3	Potassium	3.4 to 5.4 mEq/L	
			4	Calcium	8.4 to 10.6 mg/dL	
			5	Chloride	96 - 110 mmol/L	
			6	Glucose	60 to 99 mg/dL	
			7	CO2	22 to 32 mEq/L	
			8	BUN	6 to 21 mg/dL	Blood urea nitrogen
			9	Creatinine	0.4 to 1.54 mg/dL	
			10	ALP	35 to 104 U/L	Alkaline Phosphatase
			11	ALT	0 to 40 U/L	Alanine Transaminase
			12	AST	10 to 35 U/L	Aspartate Transaminase
			13	Bilirubin	0.0 to 1.4 mg/dL	
2	Urine analysis, routine and microscopic	fasting not required	14	Color	yellow	
			15	Character (Clarity)	clear	
			16	Specific gravity	1.003-1.029	
			17	PH	4.5 - 8.0	
			18	Protein	negative	
			19	Glucose	negative	
			20	Nitrite	negative	
			21	Ketone	negative	
			22	Leukocyte esterase	negative	
			23	Blood	negative	
			24	Bilirubin	negative	
			25	Crystals	negative	
			26	Bacteria/Yeast	negative	
			27	RBC/WBC/Epithelial cells	negative	
			28	Casts	negative	
3	CBC with differentials	ibid	29	RBC	$3.9-5.2 \times 10^6/\mu\text{l}$	Red blood cells
			30	MCV	80 to 100 fL	Mean Corpuscular Volume
			31	MCH	26 to 34 pg/cell	Mean Corpuscular Hemoglobin
			32	MCHC	32 to 37 g/dL	Mean Corpuscular Hemoglobin Concentration
			33	Hemoglobin	11.0-15.5 g/dL	
			34	Hematocrit	34.0-45.0 %	
			35	Platelet	$150-450 \times 10^3/\mu\text{l}$	
			36	WBC	$4.3-11.0 \times 10^3/\mu\text{l}$	White Blood Cell

* Normal value ranges may vary slightly among different laboratories, the value listed here are only for reference, the actual values will be determined by study site.

Appendix IV. Blood Metabolic/CBC and Urinalysis Tests (Continued)

#	Test Categories	Description	#	Test Items	*Reference Normal Range	Footnote
4	Urinary or serum pregnancy test**	ibid	37	Pregnancy	negative	
5	Urinary alcohol/nine panel drug screen tests	ibid	38	amphetamines	negative	
			39	cannabinoids	negative	
			40	methadone	negative	
			41	barbiturates	negative	
			42	PCP	negative	
			43	opiates	negative	
			44	benzodiazepines	negative	
			45	cocaine/metabolites	negative	
			46	methamphetamines	negative	
			47	alcohol	negative	
6	Tests for Infectious diseases	fasting not required	48	HIV Ab	negative	Human Immunodeficiency Virus Antibody
			49	HBs Ag	negative	Hepatitis B Surface Antigen
			50	HCV Ab	negative	Hepatitis C Virus Antibody
7	Thyroid Function	fasting not required	51	Free T3	200-500 pg/dL	Triiodothyronine
			52	Total T4	4.5-11.2 µg/dL	Thyroxine
			53	TSH	0.4 - 4.0 mIU/L	Thyroid Stimulating Hormone

* Normal value ranges may vary among different laboratories, the value listed here are only for reference, the actual values will be determined by study site.

** all female subjects

* Normal value ranges may vary slightly among different laboratories, the value listed here are only for reference, the actual values will be determined by study site.

** All female subjects

1. BACKGROUND

Epinephrine is an adrenal hormone and sympathetic neurotransmitter with both α - and β -adrenergic activities.

Armstrong Pharmaceuticals manufactured and marketed over-the-counter (OTC) Epinephrine CFC-MDI 220 mcg/inhalation in the U.S. for fifty (50) years, prior to discontinuation in the U.S. OTC market in 2011. The discontinuation is not due to safety, efficacy or quality issues, rather it is due to environmental consideration because of CFC propellant (Montreal Protocol).

By replacing the CFC propellant with HFA, Armstrong Pharmaceuticals is currently marketing Epinephrine HFA-MDI (internal code name “E004”) 125 mcg/inhalation under the trade name of Primatene® MIST. E004 is the only FDA approved asthma inhaler indicated for the temporary relief of mild symptoms of intermittent asthma in adults and children 12 years of age and older in the U.S. OTC market. The FDA approved Primatene Mist in 2018 under NDA 205920.

Epinephrine administered through IV/IM/SC can result in a whole array of adrenergic responses, resembling those induced by activation of the sympathetic nervous system and the adrenal glands with common adverse effects including shakiness, anxiety, sweating, fast heart rate and high blood pressure, etc.

Clinical data obtained during E004 NDA development show that after E004 administrated by oral inhalation, the systematic exposure of epinephrine is much lower than that for direct injection of epinephrine. This clinical study API-E004-CL-I is designed for a direct comparison of systematic exposure in crossover subjects among treatments of

- Epinephrine 0.3 mg (EpiPen® by [REDACTED]) by IM;
- Epinephrine 0.25 mg (Primatene® Mist) by oral inhalation; and
- Albuterol 0.18 mg (ProAir® by [REDACTED]) by oral inhalation.

2. OBJECTIVES

This study is designed to assess the drug exposure profile in systemic circulation of Primatene® Mist (0.25mg) by oral inhalation, versus Epinephrine Injection (0.30mg) by IM and ProAir® (0.18mg) HFA by oral inhalation in healthy adults.

2.1 PRIMARY ENDPOINTS

- AUC_{0-t} , defined as area under the curve (AUC) concentration curve over time, from time 0 to the time when Epinephrine reduced to the baseline post-dose for exogenous Epinephrine;
- AUC_{0-24h} , defined AUC of plasma Albuterol concentration curve over time 0 to 24 hours post-dose;
- $AUC_{0-\infty}$, defined as AUC in the plot of plasma Albuterol, or exogenous Epinephrine versus time from time 0 to infinity; and
- C_{max} , defined as the maximum plasma concentration of Albuterol, or Epinephrine.

2.2 SECONDARY ENDPOINTS

- t_{max} of Albuterol, or Epinephrine, defined as the time, at which the C_{max} is observed; and
- $t_{1/2}$, terminal elimination half-life of each analyte.

3. STUDY DESIGN AND OUTCOMES

3.1 STUDY DESIGN

This study is a randomized, safety, evaluator-blinded, single dose, three-treatment, crossover, fasting study in healthy adult volunteers. The treatments and doses evaluated in this study are summarized in Table 1.

Table 1. Treatments and Dose

Items	Treatment-A	Treatment-B	Treatment-C
Study Drug Name	Primatene Mist, E004	Epinephrine Injection Auto-Injector (Generic of EpiPen®)	ProAir
Manufacturer			
API	Epinephrine	Epinephrine	Albuterol Sulfate
Dosage Form	Microcrystalline Suspension HFA MDI	Sterile Solution	Microcrystalline Suspension HFA MDI
Strength	0.125 mg/inh	0.3mg/0.3mL	0.09 mg/inh
Dose Regimen	2 inhalations, 0.25mg	IM Injection of 0.30 mg Epinephrine in 0.30 mL	2 inhalations, 0.180 mg
Route of Administration	Oral Inhalation	IM Injection	Oral Inhalation

The study is conducted in healthy male and female adult subjects at 18 to 50 years of age with a targeted total of 24 evaluable subjects at the completion of study.

The design includes one screening visit, three (3) study visits and a follow-up phone evaluation. All subjects will be screened for enrollment before being randomly assigned to one of the six treatment sequences by 3 x 3 Latin Square method.

According to the randomized treatment sequence, each qualified subject will be treated with one of the three (3) treatments at each study visit. At each study visit, 26 PK blood samples will be collected and plasma will be isolated for analyzing concentrations of albuterol and epinephrine. The three (3) study visits, and main study procedures, are outlined in Summary of Activities below (Table 2):

The three study visits, and main study procedures, are outlined in Study Schema:

Table 2. Summary of Activities in All Visits and EOS

Study Activities & Evaluations	Screen Visit	Dosing Visit-1	Dosing Visit-2 and 3	EOS ¹
Informed Consent / HIPAA	X			
Medical history / demographics	X			
Physical Exam (PE)	X			X
Lab: Urinalysis (UA)	X			X
Lab: CBC/Comp. metab. Panel	X			X
Lab: Thyroid Function	X			
Lab: HIV-Ab, HB-sAg, HCV-Ab	X			
Inclusion/Exclusion	X	X		
Confirmation of enrollment		X		
Assign subject ID		X		
Randomization		X		
Training/Dosing of MDI	X	X	X	
Concomitant Medicines		Record throughout study period		
Urine or serum pregnancy test	X	X	X	
Urine drug screen	X	X	X	
Alcohol screen (urine or breathalyzer)	X	X	X	
Food / beverage restrictions		X	X	
Meals served		X	X	
PK Baseline samples		X (1)	X (1)	
PK samples		X (25)	X (25)	
Vital signs	X	X (6)	X (6)	X ²
12-lead ECG	X	X (4)	X (4)	X ²
Serum potassium and glucose	X	X (4)	X (4)	X ²
Adverse event reporting		Record throughout study period		

1. The fasting comprehensive metabolic panel (≥ 8 hours) for EOS will be taken at the Study Visit-3 or study termination
2. Vital signs, ECG and serum potassium and glucose at 24 ± 2 h at Visit-3 can be used for EOS

3.2 OUTCOME MEASUREMENT

3.2.1 PK Measurements

In the three study visits, PK blood samples will be taken from each subject at 26 scheduled time points (Table 3).

PK samples will be analyzed with an established and validated test method at Amphastar R&D labs.

Table 3. PK Blood Sampling Schedule

Seq. #	Scheduling	Time window	Sample No., "XX"	Seq. #	Scheduling	Time window	Sample No., "XX"
1	Baseline	within 30 min pre-dosing	01	14	40 min		14
2	1 min		02	15	50 min		15
3	2 min	± 0.5 min	03	16	60 min	±5 min	16
4	3 min		04	17	70 min		17
5	5 min		05	18	80 min		18
6	7 min	±1 min	06	19	90 min		19
7	9 min		07	20	120 min	±10 min	20
8	12 min		08	21	4 hrs		21
9	15 min	±1 min	09	22	6 hrs	±15 min	22
10	18 min		10	23	8 hrs		23
11	21 min		11	24	12 hrs		24
12	25 min	±2 min	12	25	18 hrs	±20 min	25
13	30 min		13	26	24 hrs		26

3.2.2 Data for Safety Evaluation

The following safety parameters will be monitored, documented and summarized:

- i). Vital signs, i.e., blood pressure (SBP/DBP) and heart rate (HR), at
 - Screening;
 - Pre-dose baseline, 5±2 min, 15±5 min, 60±5 min, 120±15 min and 24 ±2 hrs post-dose at dosing visits;
- ii). 12-lead ECG (Routine and QT/QTc analysis), at
 - Screening;
 - at baseline, 20±5 min, 120±15 min and 24 ±2 hours post-dose at dosing visits;
- iii). Serum glucose and potassium levels at
 - Screening;
 - at baseline, 10±2 min, 60±5 min and 24 ±2 hours post-dose at dosing visits;

- iv). Results obtained from any clinically significant findings in physical examinations, CBC, metabolic panel and urinalysis (UA) for all subjects at
 - Screening;
 - End of study evaluation.
- v). Concomitant medication record.

All subjects will be queried for adverse events (AEs) and AEs must be recorded with all related information and reported as required.

4. CALCULATION OF RELATED STATISTICAL QUANTITIES

4.1 PK/PD PARAMETERS

4.1.1 Primary Endpoints

(1) C_{max} , in units of pg/mL, is defined as the maximum of experimental data points of epinephrine or albuterol concentration for a given subject and given treatment:

[figure not shown]
$$C_{max} = \max (C_1 \cdots C_i \cdots C_n) \quad i = 1, 2, 3 \cdots n \quad (1)$$

where C_i is the observed plasma concentration of albuterol or epinephrine at the time t_i ; which is the sampling point time;
 t_1 is the baseline, and n is the number of available PK measurements.

(2) $AUC_{0-t_m}^{Tot}$ for Total API,

As is demonstrated in the left plot of **Figure 1**, the AUC is for total API, including both exogenous and endogenous, if the endogenous active ingredient exists, such as epinephrine for Treatments A and B.

Figure 1 AUC for Total Active Ingredient (left) and Drug Exposure (right)

$AUC_{0-t_m}^{Tot}$ is reported in units of pg/mL*hr, can be calculated per the trapezoidal rule as given the Eq. (2):

$$AUC_{0-t_m}^{Tot} = \sum_{i=1}^{m-1} \frac{C_i + C_{i+1}}{2} (t_{i+1} - t_i) \quad (2)$$

where

- t_m is the time of the first PK point for the subject and the treatment, after C_{max} , that is reduced to the same day baseline (C_0), if C_0 is detectable, such as for epinephrine, (see **Fig. 1**, left plot); and
- $t_m > t_{max}$, and is the smallest time point that meets

$$C(t_m) \leq C_0 + \frac{1}{2} QL \quad (3)$$

- $t_m = 24$ hrs for albuterol, or m is the number of available PK measurements until t_m .

(3) The AUC for Drug Exposure $AUC_{0-t_m}^{DE}$

The AUC for the drug exposure, as is demonstrated in the right plot of **Figure 1**, is the AUC for exogenous API, if the endogenous active ingredient exist such as epinephrine for Treatments A and B.

$AUC_{0-t_m}^{DE}$ is reported in units of pg/mL*hr, and is calculated as follows:

$$AUC_{0-t_m}^{DE} = AUC_{0-t_m}^{Tot} - C_0 t_m \quad (4)$$

where $AUC_{0-t_m}^{Tot}$ and t_m is obtained based on Eqs. (2) and (3).

(4) **Drug Exposure $AUC_{0-\infty}$** (in units of pg/mL*min) is defined as below

$$\begin{cases} AUC_{0-\infty} = AUC_{0-t_m}^{DE} & \text{if } t_m < 24 \text{ hrs} \\ AUC_{0-\infty} = AUC_{0-t_m}^{DE} + AUC_{t_m-\infty}^{DE} & \text{if } t_m = 24 \text{ hrs} \end{cases} \quad (5)$$

$AUC_{t_m-\infty}$ can be obtained per the extrapolation method as given in the Eqs. (6) –(7) below, based on the time is long enough so that

$$C(t) \approx Be^{-k_e t}, \quad (6)$$

thus

$$AUC_{t-\infty} = \int_{t_n}^{\infty} C(t)dt \approx -\frac{1}{K_e} Be^{-k_e t} \Big|_{t_n}^{\infty} = \frac{C_n}{K_e} \quad (7)$$

where $C_n = C(t_m)$ is the last available PK measurement for plasma Epinephrine or albuterol concentration, with data results greater than the analytical method's quantitation limit (QL);

K_e is the rate constant of elimination; and

B is a constant, irrelevant to time.

(5) The Elimination Rate Constant, K_e

The elimination rate constant, K_e , will be obtained using WinNonlin software.

If K_e cannot be obtained per WinNonlin (occasionally the software may not allow convergence to be achieved), or the obtained $AUC_{t-\infty}$ is 30% larger than AUC_{0-t} , then K_e for $C_1=0$ (Treatment C), will be calculated based on the least squares model from the logarithm of the last three (3) or more ($m=3, 4, 5, 6$) available PK measurements of the treatment for the subject, per the following linear equation:

$$\ln [C(t)] = a - K_e t \quad (8)$$

where $-K_e$ is the slope, and a is the intercept irrelevant to time. Then, $AUC_{t-\infty}$ will be calculated with Eq. (5).

If the baseline is greater than QL (Treatments A and B), Eq. (8) will be modified to

$$\ln [C(t) - C(0)] = a + pt \quad (9)$$

where baseline $C_1 = C(0) > 0$, the slope $p = -K_e$ can be obtained from last m data points of the given subject that are greater than the quantitative limit of the test method with least square method; where $m=3, 4, 5$ or 6 , and the obtained slope is denoted as p_m .

A consistent p_m can be accepted as the final p , for which the coefficient of variance (CV) of p_m and p_{m+1} is not more than 20%.

When m is up to 6 and $CV \leq 20\%$ is not achieved, the p_m with lowest CV with p_{m+1} will be used as the final p .

Here, m is the number of plasma samples used to calculate K_e , where $K_e = -p$.

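### Epinephrine Cmax is an observed total with no baseline-corrected companion, and SAP Eq. (1) as indexed lets the pre-dose sample count as Cmax and tmax

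*SAP*

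**What the plan says.** SAP 4.1.1 (1) says Cmax "is defined as the maximum of experimental data points of epinephrine or albuterol concentration for a given subject and given treatment". Eq. (1) takes the maximum over i = 1 to n, and t_1 "is the baseline, and n is the number of available PK measurements". SAP Table 3 places that first sample "within 30 min pre-dosing". SAP 2.2 lists tmax "of Albuterol, or Epinephrine, defined as the time, at which the" Cmax is observed. Protocol 6.2.1 and 6.2.2 read both parameters off the PK curve and set no post-dose limit.

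Elsewhere the SAP removes endogenous epinephrine. In 4.1.1 (3), the drug-exposure AUC "is the AUC for exogenous API, if the endogenous active ingredient exist such as epinephrine for Treatments A and B", and Eq. (4) subtracts C0 times t_m. For the fallback slope, 4.1.1 (5) states: "If the baseline is greater than QL (Treatments A and B), Eq. (8) will be modified to" a regression on ln[C(t) - C(0)], Eq. (9). Cmax has no such version.

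SAP 2.1 attaches the word exogenous to the epinephrine AUCs but lists Cmax only as "defined as the maximum plasma concentration of Albuterol, or Epinephrine". SAP 5.3.2.2 then names Cmax in the same bullet as AUC0-inf, after the words for drug exposure to exogenous substance.

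**The concern.** Cmax is a primary endpoint, and the protocol synopsis (V.4) has every endpoint compared across treatments. The SAP background expects far lower systemic exposure after inhalation than after injection. Adding about the same endogenous level to both sides of such a comparison makes the peaks look more alike than the drug-derived peaks are. The AUC comparison would describe exogenous drug and the Cmax comparison total epinephrine, so the two primary descriptions would not measure the same thing.

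Separately, coded as indexed, Eq. (1) can return a pre-dose concentration as Cmax, with tmax at zero or up to 30 minutes before dosing. Because t_m must be later than tmax "and is the smallest time point that meets" Eq. (3), such a profile would also end its AUC at the first post-dose sample.

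**Working it through.** **Inputs.** Protocol 1.4 gives a mean baseline of 0.23 nmol/L and peaks of 1.50 nmol/L (275 pg/mL) after 2.4 mg inhaled and 4.22 nmol/L (772 pg/mL) after 4.8 mg. The Treatment-A dose is 0.25 mg. The conversion is 275/1.50 = 183.3 pg/mL per nmol/L (772/4.22 = 182.9, consistent). The plan states no Cmax figure to reproduce.

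**Endogenous share of Treatment-A Cmax (assumes dose-linearity).**
- Baseline: 0.23 x 183.3 = 42.2 pg/mL.
- Rise from the 2.4 mg data: (1.50 - 0.23) x 0.25/2.4 x 183.3 = 24.3 pg/mL. Share = 42.2/(42.2 + 24.3) = 63%.
- Rise from the 4.8 mg data: (4.22 - 0.23) x 0.25/4.8 x 183.3 = 38.1 pg/mL. Share = 42.2/(42.2 + 38.1) = 53%.

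**Pull on an A/B ratio.** With rises a (inhaled) and B (intramuscular) and a common baseline b, the corrected ratio is a/B and the total ratio is (a + b)/(B + b). The total ratio is nearer 1 whenever a < B. The documents do not give B, so it is varied as an assumption, with a = 24.3 to 38.1 and b = 42.2:

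| Assumed B (pg/mL) | Corrected A/B | Total A/B |
|---|---|---|
| 100 | 0.24-0.38 | 0.47-0.56 |
| 200 | 0.12-0.19 | 0.27-0.33 |
| 400 | 0.06-0.10 | 0.15-0.18 |
| 800 | 0.03-0.05 | 0.08-0.10 |

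**When the pre-dose sample is the maximum.** Take a constructed profile with a pre-dose value of 80 pg/mL, entered at t = 0, and post-dose values of 61.8 at 1 min and 58.3 at 2 min, falling afterwards. Eq. (1) returns Cmax = 80 at time 0. Eq. (3) is then met at the first post-dose sample, so t_m = 1 min. Eqs. (2) and (4) give (61.8 - 80)/2 x 1/60 = -0.15 pg/mL*hr. Restricted to post-dose samples, Cmax is 61.8 at 1 min.

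**How often.** If all 26 samples were available, endogenous noise were exchangeable across them and there were no drug rise, the pre-dose sample would be highest in 1/26 = 3.8% of profiles. Any drug rise lowers that. Simulating a rise of 24 pg/mL (peak at 1 min, half-life 4 min, independent noise with CV 20-60%, all assumed) gave 0.6-3.0%, that is 24 x 0.0063 = 0.15 to 24 x 0.0301 = 0.72 profiles among 24 subjects. At a rise of 200 pg/mL the rate was at most 0.04%. The rate climbs only if pre-dose values run systematically high: a second simulation (rise 24.3 or 38.1 pg/mL, CV 20 or 30%) gave 1-8% if they are raised by 25% and 9-32% if raised by 50%. No passage suggests that they are.

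For albuterol the issue is negligible. With the 6-hour half-life in Protocol 1.4 and the shortest 2-day gap, carry-over is 0.5^(48/6) = 0.4%.

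**The case against.** The index is probably loose notation. SAP 4.1.1 (2) seeks t_m after Cmax, as the point where the curve has come back down to baseline. That presupposes a post-dose peak, and the evaluability rules in 5.1.1 protect early post-dose samples for each drug. This stands as a reason to treat the indexing as a wording repair, but the equation is what a programmer will code.

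Observed total Cmax is also a legitimate parameter. The only A/B ratio the SAP defines is relative bioavailability, on baseline-corrected AUC0-inf. No Cmax ratio or test is specified, individual curves are plotted, and each visit has its own baseline sample, so a careful reader could see the endogenous part. This limits the weight but does not supply the missing corrected value.

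The scaling is fragile. It extrapolates about 10-fold (2.4/0.25) to 19-fold (4.8/0.25) below the cited doses. The two data points also disagree on the rise per mg: 1.27/2.4 = 0.53 against 3.99/4.8 = 0.83 nmol/L. The second dose followed the first after little more than 5 minutes, yet the same baseline is subtracted. The figures can only illustrate.

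A reader might infer that the SAP labels total Cmax as exogenous. The documents do not establish that. In 5.3.2.2 the word can attach to AUC0-inf alone, since Cmax carries its own gloss there, and 2.1 omits it for Cmax. The output template, available on request, may settle it. What stands is an ambiguity between two sections.

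**Conclusion.** The concern holds as a minor point with two parts of unequal weight. The larger is that epinephrine Cmax has no baseline-corrected version although AUC and the fallback slope do, so a comparison of peaks between Treatments A and B is drawn toward 1 when the inhaled rise is comparable to baseline. The 53-63% share rests on dose-linearity, and the ratio table also rests on an assumed intramuscular rise. If the inhaled rise is well above baseline, the effect shrinks.

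The smaller part is the index in Eq. (1). A reader might infer that pre-dose values will often be reported as peaks; without a systematic pre-dose elevation, fewer than one such profile is expected among 24 subjects. Where one occurs, the effect reaches beyond Cmax and tmax: t_m falls at the first post-dose sample, and the resulting AUC0-inf and relative bioavailability are zero or negative. Nor do the documents support saying that a planned inference is invalid, because Cmax is only described.

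**What to change.** (a) Take Cmax and tmax over post-dose samples only (i >= 2 in Eq. 1).

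(b) For Treatments A and B, report Cmax - C0 beside observed total Cmax. Use the corrected value when describing exogenous peak exposure, and report values at or below zero as obtained.

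(c) Reword the 5.3.2.2 bullet to say which Cmax is meant, consistent with 2.1.

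(d) Flag any profile in which no post-dose value exceeds C0, and make the t_m rule agree with the new tmax. Leaving t_m at the first post-dose sample without comment would break the SAP's own condition that t_m exceed tmax. Either re-derive t_m from the post-dose tmax, or keep the first post-dose sample and state that the condition is waived for flagged profiles. Show mean AUC0-inf and relative bioavailability with and without them.

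The cost is SAP wording and a few lines of code; all the data are already collected. There are three downsides:
- Re-deriving t_m cannot raise the AUC of a flagged profile, because every added interval lies at or below C0. In the constructed profile t_m moves to 2 min and the AUC goes from -0.15 to -0.48 pg/mL*hr.
- Subtracting a single pre-dose sample can add variance. In the second simulation the SD was 12-19 pg/mL for Cmax - C0 against 9-15 for total Cmax with independent noise, but 10-16 against 11-17 with within-visit correlation 0.5.
- Cmax - C0 can still overstate the drug increment, because it takes a maximum over noisy samples. For a modelled rise of 24 pg/mL, the first simulation averaged 29.7 at CV 20% and 75.1 at CV 60%.

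For these reasons total Cmax is kept alongside the corrected value.

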5.3.3. Instructions to the Subjects before Dosing at Dosing Visit

- (1) No food will be allowed for 10 hours prior to dosing and until 4 hour post-dose PK samples have been collected.
- (2) Meals will be provided at normal times after the 4 hour post-dose blood draw.
- (3) Water intake is not allowed 1 hour before and 1 hour after drug administration.
- (4) All physical activities during the Dosing Visits should be limited with the exception of bathroom visits until the completion of the 120-minute post-dose PK sampling at each Dosing Visit.
- (5) The subject will remain in a semi-recumbent or seated position for 120 minutes after drug dosing. After the 120-minute PK sampling, the subject has no movement restrictions, but should refrain from any excessive physical activity.
- (6) During each Dosing Visit, subjects should refrain from alcohol consumption and caffeine-containing (including decaffeinated) beverages or foods (coffee, tea, applicable soft drinks including cola and analogs, or chocolate).

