6.2. PK Results Evaluations

6.2.1 Calculation of Primary Endpoints

- C_{max} will be obtained directly by observing the plot of PK curve;
- AUC_{0-6h} and AUC_{0-24h} will be calculated with trapezoid method;
- $AUC_{0-\infty}$ will be calculated with extrapolation method.

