4.1.2 Secondary Endpoints

- (1) t_{max} is an observed value, and is represented in units of “min”,
- (2) $t_{1/2}$, terminal elimination half-life of each analyte will be reported in this study. The half-life of elimination can be calculated using K_e :

$$t_{1/2} = \frac{\ln(2)}{K_e} \quad (10)$$

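### Epinephrine Cmax and tmax for Treatments A and B are searched over all samples to 24 h, so if Primatene's true rise is small, a late endogenous value can be reported as its peak

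*SAP*

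**What the plan says.** SAP 4.1.1(1) states that Cmax "is defined as the maximum of experimental data points of epinephrine or albuterol concentration for a given subject and given treatment". In Eq. (1) the index runs from 1 to n, where t_1 "is the baseline, and n is the number of available PK measurements". There is therefore no time window and no baseline correction, and even the pre-dose sample is in the search. Protocol 6.2.1 says that Cmax "will be obtained directly by observing the plot of PK curve", which adds no limit. Under SAP 4.1.2, tmax "is an observed value, and is represented in units of" minutes, so it inherits the same search.

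SAP 3.1 provides that at each visit "26 PK blood samples will be collected and plasma will be isolated for analyzing concentrations of albuterol and epinephrine". Of the 25 post-dose times in SAP Table 3, 19 lie at 1-120 min and six lie later, at 4, 6, 8, 12, 18 and 24 h.

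Protocol 5.3.3 keeps subjects seated or semi-recumbent for 120 min. It continues: "After the 120-minute PK sampling, the subject has no movement restrictions, but should refrain from any excessive physical activity". On food it says: "Meals will be provided at normal times after the 4 hour post-dose blood draw".

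The evaluability rules (Protocol 6.1.1, SAP 5.1.1) require the early points at 1-7 min for A and 9-21 min for B. SAP 4.1.1(3) removes the endogenous contribution from AUC in Eq. (4), but Cmax has no matching protection. Eq. (3) makes t_m, the end of the epinephrine AUC, the first return to baseline after tmax.

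**The concern.** For A and B the assay measures drug plus the subject's own epinephrine. Nineteen of the 25 post-dose samples are drawn under controlled rest. The other six are drawn when the subject may move freely, and those at 6 h and later follow the first meal. If the inhaled peak is only modestly above baseline, one ordinary late value can exceed it, and Eq. (1) would then report that value as Primatene's peak.

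Cmax is a primary endpoint and tmax a secondary one. The error also spreads. With an early peak, t_m falls within minutes and the AUC stops before the uncontrolled hours. With a late maximum, t_m moves to hours, and Eq. (5) carries the result into AUC0-inf and so into relative bioavailability. The effect is uneven, because the SAP background expects a higher exposure from the injection, which makes B harder to overtake.

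**Working it through.** The plan gives no figure for this point, so there is none to reproduce. The check has three steps.

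**1. How small could A's rise be?** Protocol 1.4 cites a six-volunteer inhaled-epinephrine study: baseline 0.23 nmol/L, peak 1.50 nmol/L (275 pg/mL) after 2.4 mg, and peak 4.22 nmol/L after a further 4.8 mg. Plasma levels were back to baseline 20 min after the second dose. The A dose is 0.25 mg. Linear scaling with dose is an assumption.

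- Unit factor: 275 / 1.50 = 183.3 pg/mL per nmol/L.
- Baseline: 0.23 x 183.3 = 42 pg/mL.
- Rise from the first dose: (1.50 - 0.23) / 2.4 x 0.25 x 183.3 = 24 pg/mL.
- Rise from the second dose: (4.22 - 0.23) / 4.8 x 0.25 x 183.3 = 38 pg/mL.
- Peak: 42 + 24 = 66 to 42 + 38 = 80 pg/mL, or 1.6-1.9 times baseline.

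**2. What does one late value do?** Apply Eqs. (1)-(4) to an A profile with a flat 42 pg/mL baseline and an inhaled rise of 24 or 38 pg/mL. The rise peaks at 2 min and decays with an assumed 4.5 min half-life. The quantitation limit QL is assumed to be 5, 10 or 20 pg/mL.

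| 6 h sample | Cmax (pg/mL) | tmax (min) | t_m (min) | AUC_DE (pg*h/mL) |
|---|---|---|---|---|
| 42 (1.0x) | 66-80 | 2 | 9-21 | 2.1-4.6 |
| 63 (1.5x) | 66-80 | 2 | 9-21 | 2.1-4.6 |
| 84 (2.0x) | 84 | 360 | 480 | 87.0-88.8 |

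The jump in the last row is the triangle around the 6 h sample: 42 x 2/2 (4-6 h) + 42 x 2/2 (6-8 h) = 84 pg*h/mL, on top of the early area. In the middle row 1.5 x 42 = 63 pg/mL stays below the 66-80 pg/mL peak, so nothing changes.

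Because t_m = 8 h is below 24 h, Eq. (5) sets AUC0-inf equal to this AUC_DE. SAP 5.3.2.3 then averages the individual A/B ratios. Suppose 24 subjects have otherwise equal ratios and one is affected:

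- 87.0 / 2.12 = 41.0, and (23 + 41.0) / 24 = 2.7.
- 88.8 / 4.56 = 19.5, and (23 + 19.5) / 24 = 1.8.

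One such profile would multiply the mean ratio by about 1.8 to 2.7.

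**3. How often?** Simulation of all 26 samples. Endogenous level: lognormal, mean 42 pg/mL, independent between samples, CV 10, 20 or 30%, multiplied by a factor in the six samples after 120 min. Inhaled component as in step 2. Entries are the share of A profiles with tmax after 120 min, over the three CVs.

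| A's rise (pg/mL) | No late rise | 25% late rise | 50% late rise |
|---|---|---|---|
| 24 | 0-10% | 7-37% | 68-76% |
| 38 | 0-4% | 0-20% | 6-49% |
| 100 | 0% | 0-0.1% | 0-1.3% |

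If only the 4-12 h samples are raised, the range over the 24 and 38 pg/mL rows becomes 0-30% at a 25% rise and 4-65% at a 50% rise.

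**The case against.** The strongest objection is that the decisive input is not in the documents. Nothing there says how far endogenous epinephrine rises after 120 min, and with no late rise the share is 0-10%. The 24-38 pg/mL figure is also weak. It scales from 15 and 30 puffs of a different strength to two puffs within 30 seconds, and the two cited doses do not agree on one slope. Drug lost during a long puff series would make the scaling understate A's peak. At a rise of 60 pg/mL the share is at most 5% with a 25% late rise and 0-19% with a 50% rise. All of this stands, and it limits what can be said about frequency.

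Control does not vanish at 120 min. Fasting runs to 4 h, and excessive activity, alcohol and caffeine stay restricted. With dosing at 07:00-11:00, the 18 h sample falls at 01:00-05:00. So the six late samples are not all drawn from active, fed subjects. This also stands.

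An observed maximum over all samples is the conventional Cmax. The study is descriptive, with no test or margin. Individual curves and parameters are plotted and listed, so a tmax of 240 min or more would be seen. The Cmax error raises A towards B, against the sponsor's expectation, so it does not flatter the product. These points lower the severity. They do not remove the error, because seeing an implausible tmax gives no rule for handling it. Re-assay of anomalies (SAP 5.2) would confirm a genuine endogenous value. Interpolation covers missing points only, and SAP 5.5.3 excludes only mistimed samples.

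**Conclusion.** The point holds as a possibility that the plan leaves open. Eq. (1) can report a late endogenous value as Primatene's Cmax and tmax, and through Eq. (3) the same value can dominate A's AUC and relative bioavailability. It matters if A's peak is about 1.6-1.9 times baseline. It nearly disappears if A's rise is 100 pg/mL or more and late levels are up by no more than 50%. The percentages rest on the assumed rise, late level, CV and half-life, none of which the plan supplies.

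Three stronger readings are tempting and are not supported:

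- A reader might infer that the reported Cmax will be wrong for many subjects. The documents give no late endogenous level, so only the possibility can be claimed.
- A reader might infer that any modest late rise enters the AUC. A 50% rise without added variability gives 63 pg/mL, below the 66-80 pg/mL peak, and leaves tmax and t_m where they were.
- A reader might infer that no drug peak can occur after 120 min. The 1-7 and 9-21 min points are evaluability rules, not stated peak times, and the cited 20 min return to baseline is for inhalation only. A later peak is not expected, but it is not excluded.

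This is a change worth making before analysis because it protects a primary endpoint cheaply. It does not invalidate the design.

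**What to change.** In SAP 4.1.1(1), 4.1.2 and 5.3.2.2, define epinephrine Cmax and tmax for Treatments A and B as the maximum, and its time, over post-dose samples up to and including the nominal 120 min draw. State that this tmax is the one used in Eq. (3). The search then uses 19 samples and also drops the pre-dose value. In the worked case with a doubled 6 h sample, it returns tmax 2 min and AUC_DE of about 2-5 pg*h/mL.

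Do not discard the later epinephrine samples. They must remain available for t_m, AUC (including the protocol's 0-6 h window), K_e and the evaluability rules, which count the 4 h point for B. List every later value above the restricted Cmax, and report the unrestricted 24 h maximum and its time as a sensitivity analysis. Keep the 24 h search for albuterol, for which the plan describes no endogenous source.

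The cost is a few SAP sentences and one extra listing. No sample or visit changes. The small downside is that a genuine drug peak after 120 min would appear only in the sensitivity analysis.
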